(i.e., other changes they have made during pregnancy), thereby countering experiences and perceptions that may make them vulnerable for substance use. Additionally, MI with its collaborative and non-confrontational approach and its emphasis on increasing awareness to successful steps towards their well-being is consistent with recommendations for brief interventions in substance use, including increasing self-efficacy and relapse prevention skill sets to extend into postpartum.

4.2. Preliminary data from R21 Along with two members of this research team, the PI conducted a RCT pilot study of 50 high-risk pregnant women attending prenatal care in a large urban clinic in Providence, RI, with comparable patient demographics to the clinical sites proposed in the current study. The intervention received very high mean ratings of satisfaction (6.3 out of 7), and the computer software was rated highly by both control and the intervention participants (4.6 out of 5). Feedback from the exit interview was positive with participants consistently reporting that they found the intervention educational, interesting, and realistic. The RCT was feasible in terms of recruitment and enrollment of participants. A total of 401 women were screened over the course of nine months, with 34% meeting eligibility criteria. Overall, of the 50 women enrolled for the randomized trial, all 50 completed the intervention session. Forty-nine women (98%) completed the booster session and assessment 4 months later, demonstrating feasibility and uptake of these sessions. Participants in the HCEM condition demonstrated a significantly larger reduction in any self-reported marijuana or alcohol use compared to control condition (time-by-group interaction $p = 0.015$). There was a higher reduction of unprotected sex at follow-up in the intervention arm than control (27% vs. 5%); the direction and magnitude of this effect was very promising and would be of clinical significance, however, was not significant with this small sample size ((OR = 0.17, $p = 0.12$); see Fig 3, right). These encouraging findings strongly support the current application. The lack of significance regarding unprotected sex reduction may also indicate that additional contact may be needed for our high-risk group of pregnant women, supporting a second booster session in the proposed trial.

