Screener items (embedded with general health questions):

1. Questions for history of STI sexual risk (i.e., number of occasions of condomless vaginal (and anal) sex in the past 30 days);
2. T-ACE (four questions) is a screen for risk drinking developed for use in OB/GYN settings;
3. Substance Use Risk-Profile Pregnancy Scale (SURP-P) (three questions) this screening is specifically designed to quickly identify obstetrical patients at risk for alcohol or illicit drug use.

Table 1. Study Measures		Antenatal		Postpartum
Self-report measures	Baseline	19-28 weeks	36-39 weeks	6 weeks
Demographic Information	X			
Marlowe-Crowne Social Desirability – Short Form	X			

Timeline Follow-back, sex, alcohol, drug use	X	X	X	X
Condom Use Self-Efficacy	X	X	X	X
Treatment Self-Regulation Questionnaire	X	X	X	X
HIV/STI Knowledge Questionnaire	X	X	X	X
Risk Perceptions Items (STI)	X	X	X	X
Importance, Readiness, and Confidence Rulers	X	X	X	X
Condom Attitude Scale	X	X	X	X
Perceived Competence Scale	X	X	X	X
COVID-19 Family Stress Screener	X	X	X	X
Objective biometric measures				
Urine or Vaginal Swab Collection: STI Testing	X*	X	X	X
Birth Outcomes				X
Hair Sample Testing (suspended 11/2022)	X**		X**	
Economic and implementation measures				
Costs Analysis	X	X	X	X
Clinic staff surveys	X			

*In-person, Michigan Medicine visits only.

**A urine sample may be collected in place of a hair sample in the event that a hair sample cannot be collected.

The following assessment measures will be administered at the baseline assessment:

1. Demographic information, including age, race, ethnicity, marital/partner status, parity, employment, socioeconomic status.
2. *Marlowe-Crowne Social Desirability Scale-Short*,¹¹⁴ includes 13 items sensitive to social desirability bias.

5.5.2 Primary Outcome Measure:

1. *Unprotected sexual occasions (USOs)* at the 8-week follow-up assessment.

USOs will be obtained from the *Timeline Follow-Back (TLFB)* to assess sex-risk behaviors at baseline and follow up assessments. The TLFB is a calendar assisted structured interview that provides a way to cue memory so that accurate recall is enhanced for event-level data; it has been used to assess sexual risk-taking. USOs will be assessed in the 90 days prior to the baseline, as well as the 8-week follow-up assessments.

5.5.3 Secondary Outcome Measures:

1. *Alcohol use and Illicit drug use*: Self-reported days of alcohol and illicit drug use at 8-week assessment.

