6.0. Retention: The research team has had retention rates (an average of 90%) in large treatment trials involving high-risk, low-income pregnant and postpartum populations. The current study will employ several approaches that we have found helpful in achieving these low attrition rates, including study staff's strong relationships with participants, efforts to value and appreciate the women's participation in the study, and frequent personal contact with the women for the duration of the study. Booster sessions will be web-based and accessible for participants to complete at home. RAs call women to remind them of their assessment appointments and maintain a list of two other people who will always know where the participant resides. Transport and childcare are provided as deemed necessary to complete assessments, particularly during the postpartum assessment. Compensation for participants' time helps facilitate retention.

A. Special circumstances affecting study retention

Because study eligibility includes being pregnant, and the HCEM is specifically tailored for pregnant women, in the event that an enrolled participant experiences a miscarriage, they will no longer be eligible for the study per the study research protocol. If study staff learns of miscarriage, study staff will call (or email if that is the preferred method of contact for the participant) the participant to follow up and offer Michigan Medicine resources for pregnancy loss, as well as notifying them of their new eligibility status.

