7.0. Data Analysis: Descriptive statistics will be calculated to summarize baseline characteristics for the full cohort and by intervention arm. Quality inspection will be carried out periodically to screen for missing-ness and data anomalies, and entry error. T-tests and chi-square-tests will be used to compare study arms with respect to demographic characteristics and baseline measures of unprotected sex and alcohol/drug use. Any identified confounders with $p \leq 0.10$ will be included in all subsequent analyses. Using the TLFB, we estimate the frequency of number of days in the 90-day period that the participant is engaged in a risky behavior. This will be carried out separately for each of the outcomes, namely, unprotected sex, illicit drug use and alcohol use, and heavy episodic drinking days (Hypothesis 1 and 2). The outcomes will be analyzed under a clustered count regression framework (Poisson or Negative Binomial) with frequency as outcome, and time (baseline, 2 months, 6 months), group (HCEM, control) and time-by-group interaction as the primary covariates. A generalized linear mixed models (GLIMMIX) approach will be adopted assigning a random subject intercept to account for the clustering within each participant. The regression model will be further controlled for potential confounders such as demographic characteristics, social desirability, and other variables that are identified to be significantly associated with outcome in the univariate analyses. We will adjust analyses for baseline pregnancy stage and assessment timing, as well as delivery status (delivered/not delivered) at follow up assessments in our data analysis, and pregnancy loss during course of study (e.g., miscarriage or stillbirth). Changes over time within each group will be estimated post-hoc by sliced effects derived from the regression model. In additional analysis, reduction in proportion of participants engaged in the risky behavior on ≥ 1 days within the 90-day period will be analyzed using a clustered logistic regression with a dichotomous outcome at the subject level indicating the status of the engagement, and with time (baseline, 2 months, 6 months), group (HCEM, control), time-by-group interaction as the primary factors. As before, a random subject intercept will account for the clustering and the model will be controlled for the same ensemble of covariates as in the case of the count regression models. Similar analyses will be conducted in the secondary aims for the outcomes that will be measured postpartum. To test hypothesis 3a and 3b, we will use structural equation modeling (SEM) approach. These include pregnancy-specific measures of autonomous motivation, self-efficacy, knowledge and risk perceptions (see Table 1). These measures are all continuous and will be measured at all three time points. All relevant direct and indirect effects will be evaluated. Significance of the indirect effect of the mediators will be tested using bootstrap method which appears to have good power in small samples. Birth outcome data will be available to the team by accessing patient medical records postpartum (Hypothesis 2c).

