7.3. Missing Data: The missing values at the subject-level will be imputed using multiple imputation (MI) methods. This will use the chained equation method that allows both categorical and continuous variables to be imputed together without making any multivariate joint distributional assumption. We will combine the results from 10 imputed datasets using Rubin's formula.¹³¹ The MI approach is valid for 'Missing at Random' scenario, i.e in cases, where the missing-ness mechanism is independent of the outcome after adjusting for covariates. Refusal to provide hair sample is perhaps one variable for which such an assumption may not be appropriate. Thus, for the models we use the information on hair sample, we will equate refusal with substance use. Based on our improved methodology for hair collection in the R21, we expect to yield $\leq 15\%$ refusal. Given that refusal is likely to be low, impact on results is likely to be small. If refusal exceeds 15%, we will conduct imputation strategies that make various assumptions about missingness and the odds that it represents. Our inability to collect hair and urine samples at remote visits for drug testing (during the COVID-19 pandemic, which began in March 2020 and is currently ongoing as of February, 2023) will result in increased missing data. Because of the difficulties in collecting samples for drug testing due to COVID-19, we suspended all collection of biological samples for drug testing for participants enrolled November 2022 and on.

7.4. Power: We estimated power based on our R21 study and calculated it using extensive simulation. For the count outcomes, power was obtained under a Poisson regression framework with time, group, and time-by-group interaction as covariates. Data was simulated 1000 times from models characterized by time and group specific means as well as the variance of the random effects estimated from the pilot data. Power was assessed for the interaction term as well as the main effects empirically by the proportion of times the corresponding coefficient was deemed statistically significant at 5% level.

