For all the outcomes, our proposed sample of 250 should be adequate for detecting small to moderate effect sizes. Even assuming the worst-case scenario of up to 20% drop-out in both arms, we plan to recruit 125 participants per arm. In our data, we observed reduction in risky behavior in both study arms; however, the reduction in the intervention arm was significantly larger. For example, for unprotected sex, the baseline average number of days of unprotected sex was 36 based on the pilot data. Assuming that the average number of days of unprotected sex drops to 32 and 29 in the control and HCEM groups, respectively, (similar to that obtained in the pilot data) at any of the follow up points, using 100 subjects per arm the difference in the reduction in the groups will be deemed as statistically significant with more than 90% power. We assume a difference of 10 days between the intervention and the control groups in the change from baseline to be clinically significant. The differences for alcohol use and drug use were more prominent in our R21 data and we anticipate to be well powered for these aims. Similar effects were obtained when the dichotomous counter-parts were simulated using a clustered logistic regression model. In our data, more than 95% of the participants at baseline were engaged in risky sexual behavior. In the proposed study, we estimate a drop by 50% in the HCEM arm, which would be statistically significant using the above sample size. Outcomes of binary alcohol/drug use also yield power above 80% for scenarios similar to those obtained in the pilot data.

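### The power of more than 90% in section 7.4 is not tied to the 8-week primary contrast; the printed figures give about 81% there

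*Combined protocol and SAP*

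**What the plan says.** Section 5.5.2 defines the primary outcome as unprotected sexual occasions "at the 8-week follow-up assessment". Section 7.0 counts days from the Timeline Follow-Back ("we estimate the frequency of number of days in the 90-day period"). It models baseline, 2 months and 6 months with a random subject intercept and a time-by-group interaction. Aim 1 in section 3.0 refers to both the 2-month and the 6-month follow-up.

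Section 7.4 obtained power from 1000 simulations under a Poisson model. These used means by time and group, together with "the variance of the random effects estimated from the pilot data". Power was "the proportion of times the corresponding coefficient was deemed statistically significant at 5% level", for the interaction and for the main effects. In the worked example, "the baseline average number of days of unprotected sex was 36 based on the pilot data", with follow-up values of 32 and 29 at any follow-up. The conclusion is that "using 100 subjects per arm the difference in the reduction in the groups will be deemed as statistically significant with more than 90% power". The 100 per arm is 125 recruited less a worst-case 20% dropout.

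Section 7.4 does not give the value of the random-effect variance. It does not say whether the means are averages over women or conditional on the random effect, and it does not say whether the interaction is tested at one visit, jointly over two, or pooled.

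**The concern.** This is the only worked power figure for the behaviour that forms the primary outcome. Because it is stated for any follow-up, it covers the 8-week visit, and a reader will apply it to the primary contrast. The printed means do not deliver more than 90% for one visit, and the inputs that might are not reported. At stake is whether the stated chance of missing the assumed effect, under 10%, is right for the primary analysis. On the printed figures it is about 19%. The recruitment target does not depend on the answer.

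**Working it through.** **Inputs.** From section 7.4: baseline mean 36 in both arms, follow-up means 32 and 29, 100 analysed per arm, Poisson model with random effects, 5% level. Assumed, because not stated: a two-sided test, means that are averages over women, and no within-woman variation beyond Poisson.

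**Effect and variance.** The interaction on the log scale is ln(32/29) = 0.09844. The random intercept cancels within woman, so for one follow-up visit the variance is V/n, with

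V = 2/36 + 1/32 + 1/29 = 0.12129.

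Power = Φ(0.09844/SE − 1.960).

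**Can the plan's figure be reproduced?** Not from the printed inputs alone. Each of these routes reaches it at 100 per arm by adding something:

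- *Both follow-ups pooled against baseline.* SE = √[(2/36 + (1/32 + 1/29)/2)/100] = 0.02974, z = 3.310, power 91.2%. A joint 2-df test of the two visits gives only 85.1%.
- *Significance at either visit, unadjusted.* The two contrasts share the baseline, so their correlation is (2/36)/V = 0.458. Power is 92.2%, but type I error is 9.2% instead of 5%.
- *Conditional means.* If the random intercept has variance v, average counts are exp(v/2) times the printed values and V shrinks by that factor. For 90%, exp(v/2) = (1.960 + 1.2816)²/2.827² = 1.315, so v = 0.548. The average baseline would then be 36 × 1.315 = 47.3 days.
- *Unrounded means.* At 32.25 vs 28.75, V = 2/36 + 1/32.25 + 1/28.75 = 0.12135, SE = 0.03484, effect = 0.1149, z = 3.30, power 91.0%.

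**One visit (8 weeks), figures as printed.**

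| Analysed per arm | SE | z | Power |
|---|---|---|---|
| 100 | 0.03483 | 2.827 | 80.7% |
| 112 | 0.03291 | 2.991 | 84.9% |
| 125 | 0.03115 | 3.160 | 88.5% |

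The row for 112 is 0.9 × 125 = 112.5, rounded down, from section 6.0: "The research team has had retention rates (an average of 90%) in large treatment trials". For 90% power, n = (1.960 + 1.2816)² × 0.12129/0.09844² = 131.5, or 132 analysed per arm. A one-sided 5% test, which the plan does not mention, gives 88.1% at 100.

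**Check by simulation at 100 per arm, average means.** The one-visit conditional Poisson test gave 79.6% to 80.6% for intercept variances from 0.05 to 1.0. A fitted random-intercept model with three time points gave 78.7% and 80.9% at variances 0.25 and 1.0. With average means, the unreported variance hardly matters.

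**Sensitivity to the Poisson assumption.** The documents give no dispersion, so these values are assumptions. Within-woman variance of 1.5 or 2 times Poisson gives 63.6% or 51.5% for one visit. Binomial variation over the 90 days, which section 7.4 does not use, gives 94.4%.

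**The case against.** The strongest defence is that 36, 32 and 29 are whole-day illustrations, described only as similar to the pilot results, while the simulation used means estimated from the pilot. Rounding alone could move one-visit power from about 47% (31.5 vs 29.49) to about 96% (means near 32.5 and 28.5). This stands. It means 81% is the power for the printed assumption, not a demonstrated correction of the sponsor's simulation.

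The one-visit reading can also be disputed. Aim 1 names two follow-ups, the model has three time points, and pooling gives 91.2%, close to what is claimed. Two passages lean towards one visit: the reference to a single coefficient, and the pilot's one follow-up ("Forty-nine women (98%) completed the booster session and assessment 4 months later"). Neither settles it, since the first covers several terms in turn and the second does not show how the new trial was simulated. However, section 5.5.2 fixes the primary outcome at 8 weeks and section 7.4 makes its claim for any follow-up, so the claim does extend to that visit.

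The conditional-mean route cannot be excluded either. It sits awkwardly with section 7.4 calling 36 an average. At variance 0.55 it would put about 11% of simulated baseline counts above the 90-day window, but the average-mean reading at the same variance already puts 5.5% there, so this separates the two only weakly.

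A reader might infer that the power simulation was done wrongly, or that the trial is too small. The documents support neither. The missing inputs could account for the stated figure, and power stays above 80% on the printed ones.

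**Conclusion.** The point holds as a minor reporting fault. For the 8-week time-by-group contrast, the printed assumption gives about 81% at the plan's worst-case 100 per arm, about 85% at 90% retention and 88.5% with nobody lost. None of these is more than 90%. This rests on average means, pure Poisson variation within woman and a two-sided 5% test. It also follows section 7.4 in counting days, whereas section 5.5.2 counts occasions. Whether the sponsor's own simulation reached more than 90% at 8 weeks cannot be judged without the inputs it leaves out.

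The sample size is not called into question. For the 10-day difference that section 7.4 regards as clinically significant, taken here as 32 vs 22, power exceeds 99% under the same model.

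Section 7.0 also leaves the choice between Poisson and Negative Binomial open. That is a separate pre-specification matter and adds nothing to this power finding.

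**What to change.** In section 7.4, do one of the following:

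- Name the 8-week time-by-group interaction as the contrast to which the power figure applies. State its power for 36 falling to 32 vs 29 as about 81% at 100 per arm and 88.5% at 125, under a Poisson model with average means and a two-sided 5% test.
- Or keep more than 90%, and report what produces it at 8 weeks: the unrounded means, whether they are average or conditional, the random-effect variance, and the contrast tested.

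Either is a short edit. The first makes the stated power less favourable; the second requires the sponsor to retrieve the simulation inputs. Neither adds participants or changes trial conduct.

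Optionally, and separately, section 7.0 could fix one count model before unblinding, with subject-level robust standard errors. Intervals may widen if the counts are over-dispersed.

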12.0. PROTECTION OF HUMAN SUBJECTS

This Human Subjects Research meets the definition of Clinical Research and of a Phase I clinical trial. It also meets the criteria of the OHRP for permitted research involving pregnant women (45 CRF, Subpart B, Part 46.204).

12.1. Risks to the Human Subjects

Human Subjects Involvement and Characteristics

Participants will include a total of 250 women in the prenatal period and their infants (details in proceeding section). Participants will be recruited from either Michigan Medicine or non-Michigan Medicine clinics. The inclusion criteria will be pregnant women (as contemporaneous as possible to first prenatal visit), age 18 or older, and will follow similar recruitment to the R21 study given feasibility and acceptability rates. Specifically, the study will include pregnant women who endorse 1) at least one unprotected vaginal (or anal) sex occasion (USO) in the past 30 days (supported by the literature for our “high risk” sample, identified as such based on childbearing age, urban, ethnically diverse, and reporting co-morbid recent history of substance use), and 2) having more than one male partner in the last 6 months and/or having uncertainty about current sexual partner’s monogamy, and 3) current alcohol/drug use risk, and 4) is receiving medical care in the state of Michigan. Exclusion criteria include: 1) inability to provide informed consent (e.g., clear cognitive impairment), or 2) inability to understand English (understand the consent form when read aloud and assessments that are narrated by computer). No women will be excluded from recruitment on the basis of race or handicap. The inability to understand English will be determined by the inclusion of a subject comprehension assessment that will consist of a brief (five-question) true/false ‘quiz’ at the end of the consent form. These questions will relate back to key issues covered in the consent (e.g., “I can quit the study once I have started?” True_False_) and will be modeled after the recommendations made by the NIH/U.S. Department of Health and Human Services. Incorrect answers will be reviewed with the participant and determination will be made regarding ability to understand English. For clinic-based or remote-based assessments, the women will receive cash, check, and/or gift cards (total equivalent to \$270) for their participation (\$5 gift card for taking the eligibility screener, \$60 for baseline session, \$20 for the first booster session, \$20 for the second booster session, \$15 for the first STI test, \$30 for completing the first follow-up assessment, \$15 dollars for the second STI test, \$30 for completing the second follow-up assessment, \$60 for completing the final follow-up assessment, and \$15 for the final STI test during postpartum). For remote-based assessments, the women will receive the same compensation amount for each session, but payments will be delivered in the form of electronic gift cards or check. Women in the prenatal period were selected for two primary reasons: (a) interventions at this juncture may take advantage of a particularly salient point in a woman’s life, in which she may be more open to considering behavior change; and (b) any positive change made has the possibility of a dual impact, on the woman’s life as well as that of her infant. Of these 250 women, 125 women will be randomized to an intervention condition (Health Check-up for Expectant Moms, a brief motivational computer-delivered intervention) and 125 to a time, attention and information-matched control condition.

Because pregnant women are a special population, we will have a DSMB (see below). During baseline and follow-up assessments, urine samples or at-home vaginal swabs will be collected so sensitive nucleic acid amplification tests can be conducted to diagnose STIs of interest (i.e., chlamydia trachomatis, neisseria gonorrhoea). When baseline and follow-up assessments are delivered remotely, the study team will direct Michigan Medicine participants to go to the clinic lab when they have scheduled prenatal visits with their provider, which requires no

physical contact with research staff. Regardless of this testing, we still plan to obtain consent to access STI results from the participant's prenatal and postpartum visits with their provider, by checking their medical chart on MiChart. The at-home STI testing kits are provided and analyzed by The Center for Innovative Diagnostics for Infectious Diseases at the Johns Hopkins University School of Medicine. They run an online outreach screening program for sexually transmitted infections (STIs) that was initiated in 2004. A kit is mailed to participants' homes with the materials needed to collect urogenital (vaginal) specimens for STI testing. Each kit includes the dry swabs needed for specimen collection, sample collection instructions, a biohazard bag for returning the specimens, a contact form, and a cardboard mailer for the specimen return (with prepaid postage). Upon return of the specimens by participants, JHU personnel log in the returned specimens, prepare them for testing, conduct the laboratory tests, verify results, and report results to the contracting organization (our research group) or directly to participants as requested. All samples obtained in the study will be used for research purposes only and will be discarded immediately upon completion of data entry and quality control procedures. While this STI testing will be performed primarily for research purposes, all results will be provided to study participants. Participants who test positive for any of the three STIs or with a recurrent STI will be referred for comprehensive STI care to their treating physician or health care provider at Michigan Medicine (if participant is a Michigan Medicine patient) to receive treatment to ensure cure. For Michigan Medicine patients, [name] (Co-I), study physician, will facilitate treatment or will refer patient to another Michigan Medicine physician who will provide treatment and counseling free-of-charge to the participant. For participants who test positive and are not Michigan Medicine patients, [name] will write a prescription for the appropriate treatment which will be available at a Michigan Medicine Pharmacy. Should they prefer to seek treatment elsewhere, research staff will do their best to help facilitate this process, and any cost of treatment outside of Michigan Medicine will be the responsibility of the participant. At the participants request, research staff will also confidentially communicate STI results to the participant's health care physician, asking the participant to sign a medical release of information for this purpose. Research staff will also follow-up with non-Michigan Medicine participants to confirm that treatment was received and/or to help identify any obstacles to treatment (e.g., if patient needs additional treatment referrals, etc.). Because both chlamydia and gonorrhea are reportable to the Michigan Health Department, they will be reported to the Health Department as required by law. We will not include genital herpes as this is not standard of care and not in the clinical guidelines for STI screening set forth by the Centers for Disease Control and Prevention (CDC). [name] will determine on a case-by-case basis for consideration of HSV serologic tests based on clinical presentation (e.g., active lesion) or partner history.

Hair samples will also be obtained at specific follow-up assessments (see Table 1). In the case that a hair sample cannot be collected, we will attempt to collect a urine sample for drug testing in its place. The hair samples will be obtained by a trained RA and will corroborate self-report of drug use in the prior 3 months. The samples will be collected from cosmetically undetectable areas on the scalp. Samples will be labeled with the study ID only, sealed, and stored into a locked cabinet in the locked research offices. They will be sent monthly by tracked mail to the Psychededics laboratory in Culver City, CA for analysis. Urine samples are collected by a trained RA at specific study visits, and will corroborate self-report of drug use in the prior 30 days. Results are read by the RA after 5 minutes, and then the sample is discarded. Results, reported by study ID, will be transferred by secure, encrypted electronic file and downloaded to a secure Michigan Medicine server. Participants enrolled after August 2022 will no longer submit hair samples.

Participants in this study are pregnant women; as such, are a federally protected population in research studies. Since the goal of this research is to develop effective interventions for pregnant women who use are at risk for STIs and substance use during pregnancy, research with pregnant women is necessary. This research meets all conditions for research involving pregnant women (45 CFR, Subpart B, Part 46.204).

Sources of Research Materials

Research materials obtained from the participants in this study will include self-report measures gathered by use of the iPad iOS (or online for remote visits), STI and hair sample testing.

